## 5.2 Obtaining informed consent

The participation of each household in the health demographic surveillance system currently in place in Mozambique is strictly voluntary and is documented by signature of the head of the household or his/her designee (person aged no less than 18 years) on behalf of all household members on an informed consent form for the registration of each household in the system. During the baseline surveillance household visit, study specific written informed consent for the COVID-19 surveillance will be requested to the household head, as also requested for other sporadic studies integrated within the HDSS (Instituto Nacional de Saude, 2016). During the same visit, a separate informed consent will be requested of individuals (or their caretakers) selected for the sero-survey. For minors we will ask informed consent from parents or guardians, for minors of 12 years or older we will also have a written assent form. In case of illiteracy, a fingerprint from the illiterate study participant and a signature from a witness (person aged no less than 18 years that is not part of the HDSS team) will be obtained in all ICFs.

At the first study visit that a household member reports symptoms that classify this person as a possible case we will ask to sign a separate informed consent form to collect nasal swabs. This informed consent will cover for this first nasal swab sampling, but also for future indicated nasal swabs up to the end of the last AfriCoVER COVID-19 household surveillance visit. For minors we will ask informed consent from parents or guardians, for minors of 12 years or older we will also have a written assent form. In case of illiteracy, a fingerprint from the illiterate study participant and a signature from a witness (person aged no less than 18 years that is not part of the HDSS team) will be obtained on all ICFs.

For household transmission investigations, a separate individual informed consent will be requested to each participating household member. Only households participating and consenting to the population-based surveillance, and where at least 50% of household members enrol can be selected for household transmission investigations.

A 10% refusal to participate will be anticipated when selecting the simple random sample of individuals for the sero-survey.

After signing the informed consent the household and/or the individual participant is free to withdraw from participation in the study at any time.

The informed consent procedure will describe the (legitimate) purpose of the study, the procedures to be followed, the risks and benefits of participation, etc. If a participant (or parent or guardian) is unable to read or write, a signature from a witness to the informed consent discussion will be obtained. Participants (or parents or guardians) will be informed that participation in the study is completely voluntary and that the participant can withdraw from the study at any time without any negative consequences. All Informed consent forms (ICFs) will be available in Portuguese and the informed consent procedure will also take place in Portuguese.

## 5.3 Specific procedures and activities

### Collection of a nasal swab for SARS-CoV-2 PCR testing

Nasal swabs will be collected through self-swabbing under supervision of trained study staff (at >1.5m distance), or by the trained study staff member (in case of children or preference by participant).

1. Write the unique HDSS household member identifier on the tube, adding: 'N\_Afri\_cover\_day' and stick a ID label from the household participant card on the tube.
2. (if the study staff is collecting the sample) Put on personal protective equipment

3. Insert the swab gently in a vertical position, 1-1.5 cm into the nostril, until there is gentle resistance
4. Rotate against the inside of the nostril for 10-15 seconds, to absorb secretions, while applying pressure with a finger to the outside of the nostril
5. Repeat the procedure in the other nostril with the same swab
6. Submerge the nasal swab in 1-3ml sterile saline or 1.5ml of UTM medium (Capricorn Scientific) in an Eppendorf tube
7. Keep in a cooled container with conditioned ice packs (0-8°C)
8. Ship within 4 hours to the CISPOC office, where samples are refrigerated at 4°C before shipping

The tubes with swabs will be stored at 2-8°C frigobox during transport to the INS lab and kept at this temperature if they can be tested within 72 hours. If a delay in testing or shipping is expected, specimens will be stored at -20°C or below. The samples can be stored at room temperature (15–30 °C) for up to 8 hours and refrigerated (2–8 °C) up to seven days until testing is performed (information from GeneXpert Instrument Systems).

#### Dried blood spot for serology on Luminex

Anti-SARS-CoV-2 antibodies will be checked on DBS based on a fingerpick. DBS are easy-to-collect in the field and experience has shown that antibodies can be detected with similar sensitivity as serum (especially with Luminex which only requires a low input amount: 1µl per sample). Furthermore, the INS staff and residents of the HDSS are more experienced in taking blood samples with a finger prick procedure, as they used this approach during previous studies (e.g. on HIV and malaria).

Blood spots will be collected through finger pricks by trained study staff.

1. Write the unique HDSS household member code on each filter paper, write a number 0 to 4, representing the sequence of surveys on the filter paper and the zipped bag, and stick a ID label from the household participant card on the zipped bag
2. Put on personal protective equipment, including gloves
3. Use a finger prick device to finger- or heel-prick blood, until a large droplet of blood forms on the skin. Apply six blood spots (75µl each) on filter paper (903 whatman protein saver cards)
4. Let the DBS sample air dry on a clean and dry surface, for 4 hours at ambient temperature
5. Store in a separate zipped bag with desiccant to reduce humidity damage (one per participant)
6. Store in a cool-box and ship at the end of the day to the central laboratory of INS or the CISPOC office, where they will be kept in a -20°C freezer.

## 5.4. Laboratory procedures and analyses

### 5.4.1 Data Collection

All participants will have unique coded identifiers for the construction of a pseudonymized database for third parties. These identifiers will be made separately for the identification of the nasal swab and Dried Blood Spot (DBS) collections of each survey. All samples will be transported to the central laboratory of the INS for analysis with the Luminex platform (serology) or 7500 (RT-PCR). Pre-analytical, analytical and post-analytical work related to the study samples will be carried out in compliance with Good Clinical Laboratory Practice (GCLP). All samples will be stored at INS and, under this protocol, only be used for the detection of coronavirus viral RNA or antibodies. Both nasal swabs and DBS will be stored long-term (5 years) at the INS for future research. Subjects will have the option to agree for this long-term storage in the ICF. Additional ethical approval will be requested if the samples will be used for screening of other pathogens or antibodies or for future research in this scientific field. If it

would be needed to ship samples to other countries, this will first be requested in appropriate MTAs and in a protocol amendment or addendum.

#### **5.4.2 Laboratory testing**

Diagnostic testing of specimens (both swabs and DBS) will be handled at the INS laboratory facilities in Marracuene in a BSL-2 laboratory using Standard Precautions. Viral inactivation (addition of the lysis buffer) of swab material will be performed in a certified Class II Type A1 or A2 biosafety cabinet during which full personal protective equipment (PPE) will be worn, such as a surgical mask, a face shield or goggles, two-pairs of gloves and an impermeable gown.

The total blood volume that will be collected for each individual participating in the serosurvey is 450 $\mu$ l by fingerprick and this will be repeated in each serosurvey round. This volume of blood will be collected on six circles of the DBS filter paper. Each of these circles takes approximately 75 $\mu$ l.

##### **A. RT-PCR for sars-Cov-2 viral RNA detection**

All collected nasal swabs will be checked for the presence of SARS-CoV-2 by real time reverse-transcriptase PCR (as described in Corman et al 2020). Depending on the prevalence in the population, RNA will be extracted from individual or pooled swabs (max 5 swabs per pool) using the available RNA extraction kit. Real-time reverse-transcription PCR will be performed under the conditions described in Corman et al 2020.

##### **B. Luminex for anti-sars-CoV-2 antibody detection**

Blood spot filter papers will be prepared by punching two discs of 4-mm diameter, and eluted overnight in 160  $\mu$ L of PBS-TBN (dilution 1:40, PBS-1 % BSA-0.15 % Tween, pH 7.4, Sigma-Aldrich). Just before use in the immunoassay, the eluted samples will be further diluted to 1:200 in PBS-BN.

We will use an in-house developed multiplex antibody assay for the detection of anti-SARS-CoV-2 antibodies, similar to the protocol described by Ayoub A et al, 2020. As a target for the detection of anti-CoV antibodies in our Luminex platform, we have selected the main immunodominant antigens of the CoV family members: the large spike glycoprotein (S) and the nucleocapsid (NC) protein. We therefore coupled recombinant NC- and S-proteins of all currently known human CoVs (all bought at Sino Biological including SARS-CoV-2, INTERCHIM, Montluçon, France) to SeroMAP microsphere beads. These beads are carboxylated polystyrene microparticles that have been colour coded into 100 spectrally distinct sets or regions. Each of these regions can be quickly distinguished by an xMAP® Instrument, which allows the interrogation of up to 100 different analytes simultaneously from only a small volume of sample (<10 $\mu$ L). Biotinylated anti-human IgG, IgA and IgM will be used to determine positivity. A cut-off value will be estimated based on a panel of negative control samples also spotted on filter paper.

Similar procedures will be conducted for testing for antibodies to other coronaviruses.

Given that cross-reactivity with malaria can be expected (common in many serological assays), we will also test all field samples for malaria using a rapid diagnostic malaria test.

#### **5.4.3 Long-term storage and destruction of specimens**

INS will be the responsible entity for long term storage of samples. The temperatures of the freezer will be monitored by the INS's central monitoring system. Participants will be asked orally and in writing on the informed consent form to consent for long term storage of samples pertaining to the study (max 5 years after final study report) for future testing. Explicit informed consent will be requested for storage of samples for future testing to objectives not covered in this protocol. Before samples will be used, approval from the sponsor and the concerned ethics committees will need to be

obtained. If a participant refused long-term storage, his/her samples will be destroyed after the submission of the final study report. Specimens stored for long-term will not be destroyed but will remain in storage at INS laboratory until instructed by the PI and laboratory coordinator.

## 6. Safety Assessment

No investigational medicinal product will be administered or evaluated in this study, nor will it include invasive diagnostic procedures apart from the dried blood spot (finger prick) sampling for the purpose of the sero-survey. For this sampling, following a finger prick, a capillary blood sample will be applied on filter paper, to generate a dried blood spot. The blood volumes required for the study are less than 2% of the total blood volume of a healthy adult person and as such too small to affect the participants health. The participant might experience some discomfort from the finger prick: he/she may transiently feel dizzy or faint and could develop a bruise or swelling (and very rarely, a local infection) at the finger prick spot.

Respiratory specimens will be collected for diagnosis of SARS-COV-2 infection by PCR during the biweekly visits as part of the surveillance. Taking these respiratory samples could feel uncomfortable but entail negligible risk to the participants health.

Establishing a Data and Safety Monitoring board (DSMB) is not applicable for this study since no investigational product or intervention will be tested.

## 7. Statistical Analyses

### 7.1 Methods

All estimated transmission or clinical outcome indicators will be adjusted for the design effect, related to the selection of HDSS enumeration areas (clusters) within the source populations. Intraclass correlation coefficients can be deducted from previous studies in the HDSS. The results of the sero-survey and social mixing survey will additionally be adjusted for age-stratified sampling.

We will calculate a incidence rate of COVID-19 disease throughout one year, adjusting for the sensitivity of SARS-CoV-2 RT-PCR on nasal swabs by delay between symptom onset and testing. Using the longitudinal sero-survey data, determining the proportion of asymptomatics, we will be able to adjust the clinical incidence rate to a SARS-CoV-2 infection incidence rate, and determine the SARS-CoV-2 infection annual attack rate and the infection fatality risk by age group.

We will undertake three risk factor analyses: of SARS-CoV-2 infection, of COVID-19 disease (symptomatic infection), and of COVID-19 hospitalisation and death (severe disease). Using negative binomial regression, we will investigate the association with socio-demographic factors, clinical characteristics such as underlying medical conditions, and uptake of preventive measures. We also investigate the association between SARS-CoV-2 infection (from the sero-survey) and recent exposure, contact and mobility patterns (from the social mixing questionnaire).

We will assume everyone will be susceptible initially and basic and effective reproductive numbers ( $R_0$  and  $R_e$ ) will be calculated by the rate of change of incidence over successive serial intervals (time between onset of infection of index and onset of infection of infected).

We will use established methods (Cauchemez et al 2004; te Beest et al 2013) to estimate generation time distribution, ratio of transmissibility between symptomatic and asymptomatic cases, duration of

the infectious period, and the basic reproduction number, from the transmission data collected in households.

We will include heterogeneity in these parameters as far as possible, e.g. focus on the difference in transmissibility between children and adults. How much heterogeneity can be included in the estimation procedure will depend on the quality of the collected data. The estimation procedure will provide an estimate of the basic reproduction number, possibly composed of within household transmission and between household transmission, depending on the observations. These parameter estimates will be used to inform a compartmental model that describes the spread of SARS-CoV-2 on the population level. We have developed such models for the situation in the Netherlands (Teslya et al 2020) and are currently extending this modelling approach to include age structure of the population. The model can be fitted and/or validated using reported numbers of cases on the national level and estimates of attack rates in the population obtained from the repeated sero-surveys. We will develop scenarios of possible interventions in collaboration with local partners from Mozambique and use our models to project the possible impact of such interventions when rolled out in the population.

We have also developed a modelling approach that allows an assessment of the impact of social distancing and contact tracing on the doubling time of an outbreak (Kretzschmar et al 2020). This modelling approach was built on earlier work in modelling of outbreak response (see Kretzschmar et al 2004; Bonacic Marinovic et al 2014; 2015). In this work we have developed a framework to quantify timeliness of response based on disease specific parameters such as the generation time interval and proportion of secondary infections that are generated before symptom onset by an infectious case. We will explore whether data on contact tracing from Mozambique can be used to assess its impact on epidemic spread, and to derive guidance on how timely and complete tracing of contacts has to be so that it can be used as a tool to slow down or even contain the epidemic.

We will derive brand-specific total vaccine effectiveness against infection and against disease, in respectively a case-cohort design and a cohort design. Total vaccine effectiveness is the protection of vaccinees due to direct effects and added protection of vaccinees owing to vaccination of their neighbors or contacts, while overall vaccine effectiveness considers protection of an entire population, irrespective of the vaccination status of its individual members, due to the combination of total protection and protection of non-vaccinees due to vaccination of their neighbors or contacts (Ali et al 2015). To derive total vaccine effectiveness against infection, we will compare the proportion of sero-survey participants who seroconverted in the past 3 months among vaccinated against the proportion in non-vaccinated, adjusting for age and sex and other confounders. To derive total vaccine effectiveness against disease, we will compare the odds of vaccination among symptomatic confirmed SARS-CoV-2 cases detected through the population-based surveillance with the odds of vaccination among sero-survey participants who did not seroconvert in the past 3 months, in a case-cohort design. We will also explore overall vaccine effectiveness against disease using regression models comparing housing blocks with different levels of vaccination coverage among sero-survey participants.

We will estimate the conventional data-based secondary attack rate, which is the proportion of seroconversion among identified household contacts. However, these are not necessarily all secondary infections from the household index case, and could be tertiary. Therefore we will also derive a model-based secondary attack rate, estimating the number of actual secondary infections of the household index case. To do so, we could use a chain-binomial statistical model, as described by Jing et al (doi:10.1016/S1473-3099(20)30471-0), with an expectation-maximisation algorithm to account for (a) uncertainty in the infection time of asymptomatic infections, for (b) an incubation and infectious period distribution, as described in literature, and consider (c) the timing of symptom onset in

symptomatic household contacts and (d) the age-specific proportion of asymptomatic infections as estimated from the active population-based surveillance and sero-survey.

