Immune factors may affect community transmission. Cross reactivity with existing endemic coronaviruses, (CoVs 229E, NL63, HKU1,OC43), two of which are related beta-coronaviruses (HKU1,OC43), could result in protection from infection and/or disease. Many models assume a person can no longer be infected once recovered (Fig 1). However, immunity to coronaviruses is unclear. Antibody titer to SARS-CoV-1 infection waned over a period of several months in recovered patients (Liu et al 2006), but unclear if this means waning protection. Additionally, endemic human coronaviruses existing neutralising antibodies may not sufficiently protect against reinfection (Callow et al 1985), while some reports of reinfection with SARS-CoV-2 have been reported, though none fully documented.

[figure not shown]

Fig 1. Susceptible-Infected-Recovered Model

In the first few weeks of 2021, vaccines under WHO's Emergency Use Listing have begun to be used in several countries and plans exist to roll out one or more vaccine types in Mozambique. Vaccine effectiveness studies are key to better understand how these vaccines perform in different settings, especially since the emergence of SARS-CoV-2 variants circulating in Mozambique against which several current vaccines may not protect.

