Active syndromic population surveillance (biweekly) with PCR testing of symptomatic individuals – 12 months	15393 individuals (2108 households) Possible cases reporting any respiratory sign or loss of smell or taste, with or without fever, selected for PCR testing. Initially, before widespread community transmission, pooled testing of possible cases; when >50 confirmed cases per week, switch to PCR testing of 1 in 10 possible cases (systematic selection - every 10th possible case)	
 
● COVID-19 disease incidence rate (symptomatic infections per person-month)
 
● COVID-19 related hospitalisation rate
 
● Case (disease) fatality risk (%)
 
● Risk factors for severe outcome/hospitalization
 
● Basic reproduction number
 
● Effective reproduction number
 
● Serial interval
 
● Proportion uptake of measures to prevent infection; barrier uptake
 
● Effectiveness of interventions
 

		
 
• COVID-19 incidence density maps
 
• COVID-19 likelihood ratios of clinical signs
 
• Brand-specific vaccine effectiveness against confirmed COVID-19 (disease)
 

Age-stratified sero-survey at 0, 3, 6, 12 months	2400 individuals/dried blood spot samples per round (800 per age group <18yo, 18-50 yo, >50yo) An age stratified sample of individuals will be selected (simple random sample in each age group)	
 
• SARS-CoV-2 infection annual attack rate (%)
 
• Infection fatality risk
 
• Proportion asymptomatic infections, by age group
 
• Risk factors for infection
 
• Association between antibody titers and reinfection
 
• Brand-specific total vaccine effectiveness against SARS-CoV-2 seroconversion
 
• Overall vaccine effectiveness against SARS-CoV-2 seroconversion
 

Repeated social mixing survey	the same 2400 individuals selected for the sero-survey (800 per age group <18yo, 18-50 yo, >50yo)	
 
• correlation between number of contacts, intensity of contacts and attack rate
 
• correlation between uptake of control measures and attack rate
 
• social contact matrices to be used to parametrize dynamic transmission models
 

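### Sero-survey estimates, including the primary attack rate, have no planned correction for error of the in-house antibody assay or for loss of antibody

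*Combined protocol and SAP*

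**What the plan says.** Section 7.1 adjusts every indicator for the design effect and adds, for the two surveys: "The results of the sero-survey and social mixing survey will additionally be adjusted for age-stratified sampling". For disease incidence it goes further, "adjusting for the sensitivity of SARS-CoV-2 RT-PCR on nasal swabs by delay between symptom onset and testing". The sero-survey then supplies the asymptomatic proportion, which 7.1 uses to move from clinical incidence to infection incidence, attack rate and infection fatality by age. Table 1 marks the "SARS-CoV-2 infection annual attack rate" as a primary outcome of the sero-survey.

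For VE against infection, 7.1 states that "we will compare the proportion of sero-survey participants who seroconverted in the past 3 months among vaccinated against the proportion in non-vaccinated", with adjustment for age, sex and other confounders. The data-based household secondary attack rate is also a proportion of observed seroconversions.

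On the assay, section 5.4.2 B says: "A cut-off value will be estimated based on a panel of negative control samples also spotted on filter paper". It adds: "Given that cross-reactivity with malaria can be expected (common in many serological assays), we will also test all field samples for malaria". No section says how the malaria result enters an analysis. The Background notes, for a related virus: "Antibody titer to SARS-CoV-1 infection waned over a period of several months in recovered patients". Neither 5.4.2, 7.1 nor 7.2 gives a sensitivity, a specificity or a correction for the Luminex result.

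**The concern.** The plan accepts that test error matters for PCR and handles it for disease incidence, but takes the antibody result at face value. An observed seropositive or seroconversion proportion mixes true infections that were detected, infections that were missed or whose antibody has faded, and false positives. The error passes from the attack rate into the asymptomatic proportion, infection fatality and the transmission model, which 7.1 says may be fitted or validated on sero-survey attack rates. For VE, false positives that arise equally in vaccinated and unvaccinated people pull the estimate towards zero, most strongly when true seroconversion is rare, as in the 5% over 3 months that 7.2 assumes.

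**Working it through.** **Inputs.** From 7.2: attack rate 40%, margin 3 points, 800 per stratum; half of infections symptomatic and case fatality 2%; 2,400 participants with 20% coverage (480 vaccinated, 1,920 not), seroconversion 5% over 3 months and 10% over 6, VE 50%. Assumed, because the documents give none: Se 0.85 to 0.95, Sp 0.98 to 0.995. Wider values are labelled where used.

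**1. The plan's own figures.** Half-width at 40%: 1.96 × √(0.4 × 0.6 / 800) = 3.4 points, or 3.1 with a finite-population correction for an assumed stratum of 15,393/3 = 5,131. The plan states 3. Power for 2.5% v 5% and 5% v 10%: 64.3% and 95.2% (exact, Yates-corrected chi-square) or 68.8% and 96.2% (pooled normal). The plan states 66% and 97%. These calculations enter true rates, so they assume an error-free assay.

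**2. Observed proportions.** Observed = p × Se + (1 − p) × (1 − Sp). At p = 0.40, Se 0.85 and Sp 0.995 this is 0.340 + 0.003 = 34.3%. With false positives independent between rounds, the same formula approximates observed seroconversion, and observed VE = 1 − observed(p1)/observed(p0), with p0 = 0.05, p1 = 0.025 for 3 months and 0.10, 0.05 for 6. It ignores earlier infections missed at the previous round.

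| Se | Sp | Attack rate 40% reads | VE 50% reads, 3 months | VE 50% reads, 6 months |
|---|---|---|---|---|
| 0.85 | 0.98 | 35.2% | 33.7% | 40.3% |
| 0.85 | 0.995 | 34.3% | 44.7% | 47.2% |
| 0.95 | 0.98 | 39.2% | 35.0% | 41.2% |
| 0.95 | 0.995 | 38.3% | 45.2% | 47.5% (47.49) |

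The bias in the attack rate runs from 0.8 to 5.7 points.

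**3. VE with persistent false positives.** A person who cross-reacts at every round is already positive at the earlier one and cannot convert. If a share f does so in both groups, observed conversion is (1 − f) × Se × p in each. Both factors cancel, and VE reads 1 − 0.025/0.05 = 50%.

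**4. Power.** By the pooled normal method at Se 0.90: 43.8% and 85.7% with Sp 0.98 and independent false positives; 63.2% and 93.8% with Sp 1.

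**5. Derived quantities.** At 7.2's values 20% of the population have symptomatic infection and 0.4 × 0.5 × 0.02 = 0.4% die. If infections come from a single-round reading and cases from corrected surveillance, the asymptomatic share reads 1 − 20/34.3 = 42% to 1 − 20/39.2 = 49% instead of 50%. Infection fatality reads 0.4/39.2 = 1.02% to 0.4/34.3 = 1.17% instead of 1.0%.

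**6. Antibody loss.** With an otherwise perfect assay, loss in an assumed 10 to 30% of infected people takes a single-round reading from 40% to between 36% and 28%. With 20% loss, Se 0.90 and Sp 0.98: 0.32 × 0.90 + 0.68 × 0.02 = 30.2%.

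**7. Counting anyone ever positive.** At Sp 0.98 with independent errors, three follow-up rounds mislabel 1 − 0.98³ = 5.9% of uninfected people, which adds 0.059 × 60 = 3.5 points at a 40% attack rate.

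**8. Cost in precision.** The Rogan-Gladen estimate is (observed + Sp − 1)/(Se + Sp − 1), so the half-width is divided by Se + Sp − 1. At n = 800: Se 0.95, Sp 0.99 gives 1.96 × √(0.386 × 0.614/800)/0.94 = 3.6 points; Se 0.80, Sp 0.97 gives 1.96 × √(0.338 × 0.662/800)/0.77 = 4.3 points. Both take Se and Sp as known.

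**The case against.** Several points on the other side stand.

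- **Every assay figure is assumed.** So the sizes are illustrations. The need to prespecify a correction does not depend on them.
- **The laboratory plan has safeguards.** The assay targets "the large spike glycoprotein (S) and the nucleocapsid (NC) protein", includes the other human coronaviruses, and is called newly validated in 1.2. Every field sample gets a malaria test, and antibody titers over time are a secondary objective. These may keep the error small and supply what a correction needs, but none enters an estimator.
- **VE bias is not certain.** A reader might infer that cross-reactivity must pull VE down to 34 to 45%. The documents do not support that: cross-reactivity that persists within a person does not count as conversion (step 3). Low sensitivity alone, equal in both groups, also leaves VE unbiased and costs only power.
- **The attack-rate estimator is not defined.** A reader might infer that the plan reports month-12 seroprevalence. It does not say so; 7.1 describes scaling clinical incidence by the asymptomatic proportion. Serology error can still enter through that proportion (step 5).
- **Antibody loss is raised only in background text on SARS-CoV-1.** That makes it plausible but says nothing about its size here.
- **Other adjustments exist.** Design effect and confounder adjustment are planned as well as age sampling, and the PCR correction is stated for disease incidence only. Neither of the first two deals with assay error.
- **Specificity may differ by vaccination status.** Spike is one of the antigens. If vaccination itself raises that antibody, a correction with one common specificity would not repair VE, and the definition of seroconversion in vaccinees must be settled separately.

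**Conclusion.** The omission is real and worth correcting before analysis. The plan relies on an in-house antibody result for a primary outcome and several derived ones, anticipates cross-reactivity, and corrects none of them for assay error or antibody loss.

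On the assumed Se and Sp, the single-round bias in a 40% attack rate lies between less than 1 point and nearly 6, so it can, but need not, exceed the planned 3-point margin. Antibody loss would lower a single-round reading further. For VE against seroconversion the supportable statement is a range that includes no bias at all. Its lower end requires false positives that are independent between rounds and equally common in both groups, and the documents do not settle either condition.

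**What to change.** State in 7.1 that the attack rate, asymptomatic proportion, infection fatality, VE against seroconversion and household secondary attack rate will be corrected for assay sensitivity and specificity, with their uncertainty carried through.

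- **Method.** Rogan-Gladen for single-round prevalence. For seroconversion and the cumulative attack rate, a Bayesian or latent-state model over the repeated rounds that allows for antibody loss and for within-person correlation of false positives.
- **Definition.** Define the annual attack rate. Do not use an uncorrected ever-positive count: it limits the effect of antibody loss but accumulates false positives (step 7).
- **Specificity.** Use negatives that did not set the cut-off, for example held-out or cross-validated panel samples, and examine it by malaria test result. Specificity measured on the samples that set the cut-off is optimistic.
- **Sensitivity by time since infection.** Use PCR-confirmed participants with later blood spots. Table 3 already provides these for index cases and for contacts, including asymptomatic contacts found by PCR, but only to day 28 after onset in the index case. Later times must come from confirmed cases who are also in the sero-survey. Because surveillance swabs symptomatic people, add a sensitivity analysis with lower sensitivity in asymptomatic infections.

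The cost is analysis work and wider intervals: about 3.6 to 4.3 points half-width against 3.4 at n = 800, over Se/Sp of 95/99% to 80/97%. Uncertainty in Se and Sp widens them further, by an amount that depends on panel sizes the documents do not give. No extra visits or participant samples are needed.
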